8. RESEARCH QUESTION AND OBJECTIVES

The purpose of this study is to evaluate the post-discharge treatment patterns including persistence and outcomes such as recurrent VTE and bleeding among hospitalized adults with VTE treated with apixaban or warfarin.

The study objectives are to:

1. Describe the proportion of patients with VTE treated with apixaban or warfarin in the hospital
2. Understand the post-discharge treatment patterns (including persistence, switch, and discontinuation) among patients who started on apixaban or warfarin in the hospital

The secondary objective is to:

3. Assess recurrent VTE, major bleeding, and clinically relevant non-major (CRNM) bleeding among patients who continue on apixaban or warfarin in the outpatient setting while persistent on index therapy

[figure not shown]

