9.1.2. Exclusion criteria

Patients meeting any of the following criteria will be excluded from the study:

1. Patients with hospitalization with a primary diagnosis of VTE in the 6-month pre hospitalization period
2. Patients with any OAC administration other than apixaban for apixaban cohort (except warfarin use before apixaban) or warfarin for warfarin cohort during hospitalization

Note: Apixaban cohort patients will be allowed to have warfarin prior to apixaban administration. At this step, we will also report the number of patients that have both apixaban and warfarin use during the hospitalization.

3. Patients with unfractionated heparin or low molecular weight heparin (LMWH) administration after apixaban (for apixaban cohort) or warfarin (for warfarin cohort) administration during hospitalization.

Note: that unfractionated heparin or LMWH prior to apixaban or warfarin will be allowed.

4. With ≥ 1 claim/record with a diagnosis code for atrial fibrillation/flutter in Dx or CDM during the hospitalization and in the 6-month pre hospitalization period
5. With ≥ 1 claim with a procedure code for mechanical heart valve in Dx or CDM during the hospitalization and in the 6-month pre hospitalization period
6. With ≥ 1 claim with a procedure code for inferior vena cava filter in Dx or CDM during the study period
7. With ≥ 1 claim with a diagnosis code or procedure code of pregnancy in Dx or CDM during the study period
8. With use of OAC or PAC (in LRx or Dx) (unless prophylactic) during the 6-month pre-hospitalization period

Note: The OAC or PAC prescription claim will be considered prophylactic if duration of the prescription is ≤ 42 days AND the start date of OAC or PAC occurs within 2 days before or 7 days after knee/hip replacement surgery

OR

Start date of OAC or PAC occurred within 7 days after the admission of a hospitalization associated with 'medically ill' (primary discharge diagnosis; codes provided separately) AND with a ≥ 3 -day length of stay of the hospitalization.

9. With data quality issues (invalid/missing enrollment dates, gender and payer type)

A preliminary attrition table will be provided to the Alliance for review, at which time modifications to the inclusion and exclusion criteria may be considered.

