9.3. Data sources

IQVIA's CDM database will be linked to Dx and LRx for this analysis.

Hospital Charge Data Master (CDM)

IQVIA's Hospital CDM is comprised of hospital-based data which are sourced from hospital CDM files that roll up to the UB-04 files which are submitted for payment. Data covers non-federal, acute-care short-stay hospitals, covering inpatient and outpatient services, including emergency room (ER) utilization with information on diagnoses, procedures, treatment and daily un-adjudicated charge details. Limited patient and hospital characteristics are also available. Data is available from 2001, with a data lag of approximately 6 weeks. The data cover more than 450 hospitals per month and approximately 8 million inpatient visits and 105 million outpatient visits per year. Charge details during a stay are provided on a daily basis (and lack a time stamp). Diagnoses lack a time or day stamp.

It is important to note some limitations of this dataset. Firstly, because this is an open-source database, there is a loss of visibility to healthcare activity and consumption outside of hospitals that participate in/contribute to the database. Secondly, unlike administrative health plan claims data, it is not possible to apply continuous enrollment (CE) requirements. Proxies for CE must be implemented based on hospital reporting to provide greater assurance that patient healthcare activity within this database is captured during the study period. Socioeconomic details, such as race/ethnicity or income, are unavailable in the data. Clinical detail is also limited. Due to patient privacy reasons, a subject who is 85 years or older will only have the recorded age of "85". And finally, only charges are available in CDM, thus a national cost to charge ratio must be applied to charges.

Medical claims (Dx) database

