IQVIA's Dx database captures over one billion pre-adjudicated claims and three billion records obtained annually from approximately 800,000 office-based physicians and specialists. Dx database is updated on a weekly basis with approximately a 30-60 day lag for data completeness. Key information includes International Classification of Diseases, ninth revision, clinical modification (ICD-9-CM) and International Classification of Diseases, tenth revision, clinical modification (ICD-10-CM) diagnoses, CPT/procedure/Healthcare Common Procedure Coding System (HCPCS) for medical conditions and procedures, date of service, location of care, (pre-adjudicated) charged amount for service, payer types (commercial, Medicaid, Medicare, cash payment), patient age and sex. Note that inpatient data is limited.

Longitudinal Prescription Claims (LRx)

IQVIA LRx database captures information on dispensed prescriptions sourced from retail, mail, long-term care, and specialty pharmacies. These suppliers have direct, long-standing relationships with IQVIA, with many providing data on a daily basis, and all suppliers support weekly data feeds with an ability to provide insight within ten days of the end of each week. This enables IQVIA to ensure that the LRx database has good longitudinal, representative, and current data from consistent and stable suppliers. IQVIA has industry-leading coverage in the following channels: 92% coverage of the retail channel, 72% coverage of standard mail service, and 76% of long-term care facilities. IQVIA receives specialty data directly from the pharmacy resulting in near census data coverage, contributing to greater precision for longitudinal analysis. Additionally, diagnosis is included directly on the majority of specialty pharmacy transactions from the specialty pharmacy providers. An important strength of the LRx database for this analysis is the longitudinal capture of adjudicated and cash prescriptions for all age categories, regardless of insurance type.

Linkage Methodology

A proposed dataset will be constructed utilizing patient data from LRx, Dx and CDM, with the appropriate dataset being selected based upon proportion of linked patients. This process which is compliant with The Health Insurance Portability and Accountability Act of 1996 (HIPAA) is described below:

- IQVIA has developed a patented and proprietary encryption algorithm that utilizes actual patient-level information to create a unique Patient identifier (ID)⁸

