9.8. Limitations of the research methods

This study will have limitations inherent to observational studies involving claims and hospital charge data, as well as limitations related to the study design. Results from retrospective studies must be interpreted with caution and can only establish associations and not cause-and-effect relationships.

Claims data do not provide as much clinical detail as medical records as they are primarily collected for the purposes of payment. Therefore, there is a potential for miscoding or misclassification (e.g., identification of newly treated VTE patients). There is also the potential for under-coding if they are not captured for billing purposes.

Because these are open-source databases, there is a loss of visibility to healthcare activity/consumption at pharmacies, offices and hospitals that do not participate/contribute to the databases. Pharmacy stability requirements will be applied to the index prescription pharmacy at the patient level. Nevertheless, LRx has high prescription coverage (e.g., 63% of retail pharmacies in the US). Over-the-counter products will not be captured.

Unlike administrative health plan claims data, it is not possible to define periods of continuous enrollment (CE). Only proxies can be implemented based on patient activity and pharmacy stability to provide greater assurance that patient healthcare activity within these databases is captured during the study period. The data also lack information on mortality.

Only patients with a hospitalization or outpatient visit to a hospital in the CDM database are present in the CDM database, therefore potentially representing a more severe population.

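### Criterion 8 does not search the linked hospital charge file (CDM) for earlier oral anticoagulant use, so some prior users visible in the study's own data can enter as in-hospital starters

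*Combined protocol and SAP*

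**What the plan says.** Objective 2 (section 8) concerns treatment patterns "among patients who started on apixaban or warfarin in the hospital". Inclusion criterion 2 (section 9.1.1) takes the first administration in the index stay as the start of treatment.

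Whether that start is really new depends on exclusion criterion 8 (section 9.1.2): "With use of OAC or PAC (in LRx or Dx) (unless prophylactic) during the 6-month pre-hospitalization period". Its note exempts two kinds of prophylactic use:
- prescriptions of up to 42 days that begin around knee or hip replacement;
- use that begins within 7 days of a medically-ill admission lasting at least 3 days.

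The neighbouring criteria name other sources. Criterion 4, for example, looks for a "diagnosis code for atrial fibrillation/flutter in Dx or CDM during the hospitalization and in the 6-month pre hospitalization period", and criteria 5 to 7 also name Dx or CDM.

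Section 9.3 describes the three files:
- CDM covers hospital inpatient and outpatient services, "including emergency room (ER) utilization with information on diagnoses, procedures, treatment and daily un-adjudicated charge details".
- LRx "captures information on dispensed prescriptions sourced from retail, mail, long-term care, and specialty pharmacies".
- Of Dx, the protocol says: "Note that inpatient data is limited".

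Section 9.8 concedes that "there is a potential for miscoding or misclassification (e.g., identification of newly treated VTE patients", but does not mention this gap.

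**The concern.** An OAC given at an earlier hospital visit is the kind of record that CDM holds, and that LRx and Dx are least likely to hold. Criterion 8 passes over it. The linked file can therefore contain direct evidence of use in the 6 months before admission while the analysis counts the same patient as a new starter.

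What is at stake is the meaning of the cohort in objective 2. Persistence, bleeding and recurrence may differ between people resuming a drug and people beginning it. The Cox models in section 9.6 also take treatment cohort as the main effect, so a different share of prior users in the two cohorts could move the hazard ratios.

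**Working it through.** **Text check.** Sources named for each rule that bears on prior use:

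| Rule | Period | Source named |
|---|---|---|
| Exclusions 2 and 3 (other OAC; heparin after the index drug) | Index stay only | None named |
| Exclusions 4 and 5 | Index stay and prior 6 months | Dx or CDM |
| Exclusions 6 and 7 | Whole study period | Dx or CDM |
| Exclusion 8 (prior OAC or PAC) | Prior 6 months | LRx or Dx |

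No other section searches CDM for anticoagulants before the index admission.

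**Do other rules close the gap?**
- Exclusion 1 removes earlier stays with a primary VTE diagnosis only. A stay with VTE as a secondary diagnosis, or an ER visit, passes.
- Inclusion 5 asks for one Dx claim and one LRx claim of any kind. It does not show that anticoagulant fills would be seen.
- Pharmacy stability (section 9.2, item 1b) tests only the pharmacy of the treatment index fill, not one used earlier.

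These rules narrow the gap but leave it open.

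**Size.** The plan gives no figure to reproduce, so this is an illustration.

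Inputs:
- p = share of otherwise eligible patients with a prior CDM OAC charge; assumed 1% to 10%.
- c = chance that LRx or Dx also shows the use; 0, 0.63 or 0.92. The last two borrow the retail coverage figures of sections 9.8 (63%) and 9.3 (92%) as proxies. Those two figures need to be reconciled or their bases explained.
- d = persistence in prior users minus persistence in new users; assumed −20 to +20 percentage points.

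Residual share of prior users after criterion 8: f = p(1 − c)/(1 − pc). Shift in the proportion persistent = f × d.

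| p | c | f | Largest shift (d = ±20 points) |
|---|---|---|---|
| 1% | 0 | 1.0% | ±0.2 points |
| 1% | 0.63 | 0.0037/0.9937 = 0.4% | ±0.07 points |
| 1% | 0.92 | 0.0008/0.9908 = 0.1% | ±0.02 points |
| 10% | 0 | 10.0% | ±2.0 points |
| 10% | 0.63 | 0.037/0.937 = 3.95% | ±0.8 points |
| 10% | 0.92 | 0.008/0.908 = 0.9% | ±0.2 points |

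**Direction.** Post-discharge use is also read only from LRx (sections 9.2 and 9.2.2). A patient with a CDM charge but no LRx or Dx trace could be any of these:
1. Someone who fills outside LRx before and after the stay. This patient is counted as having no outpatient OAC claim, which lowers apparent continuation, and never enters the persistence estimate.
2. Someone who fills once in LRx and then returns to the outside pharmacy. The 30-day gap rule counts this patient as discontinued, which lowers persistence.
3. An established user who is invisible before admission and visible after it. This patient might raise persistence.
4. Someone with brief in-hospital use only. The effect could go either way.

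Persistence is counted from the treatment index date after discharge, so earlier days of use are not added to it. The documents give no mix of these types, so the sign cannot be determined.

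**The case against.** The strongest reply is that the gap is narrow and the plan is consistent. Criteria 4 to 7 concern diagnoses and procedures. For baseline drugs, section 9.2.1 also uses LRx or Dx, so criterion 8 follows a convention. Most continuing outpatient users would be caught by LRx. CDM sees only contributing hospitals. The attrition review in section 9.1.2 allows the criteria to be changed, and section 9.8 discloses misclassification. All of this stands as a reason to expect small numbers. It does not justify leaving the evidence unused: the list in section 9.2.1 only describes patients, whereas criterion 8 decides who counts as a starter.

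A second reply also stands: adding the letters CDM is not enough. The surgical exception relies on a prescription duration, which the described CDM data (daily charges) do not show. The medically-ill exception could exempt a home OAC that was merely continued during such a stay.

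A reader might infer that the gap inflates persistence, lowers early bleeding and does so more for warfarin. The documents do not support this, because types 1 and 2 above pull the other way and nothing is said about prior use by cohort. One can construct an upward shift, but only by assuming it:
- Let 35% of admissions be prior users. Let 30% of these use a second pharmacy, and let 37% of those pharmacies not report. The unseen fraction is then 0.30 × 0.37 = 0.111.
- Unseen prior users are 0.35 × 0.111/(0.65 + 0.35 × 0.111) = 5.6% of the cohort.
- With persistence of 85% in prior users and 55% in starters, the estimate is 0.944 × 55% + 0.056 × 85% = 56.7%, a shift of 1.7 points.

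The prior-user share, the second-pharmacy share and both persistence rates are assumed; the 37% is the complement of the 63% coverage figure. The 5.6% covers all unseen prior users, not those whom CDM would reveal. If CDM revealed 10% to 30% of them (also assumed), about 0.2 to 0.5 points would be attributable to this gap.

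**Conclusion.** The point holds as an incomplete new-user definition. Criterion 8 leaves out a linked source that can show prior OAC use, and no other rule makes up for it. The number of patients affected is probably small. Under the assumed ranges, the shift in the proportion persistent is at most 2.0 percentage points either way, and at most 0.8 points if LRx or Dx catches 63% of such patients. The size and direction of any effect on persistence, bleeding or the cohort hazard ratios are unknown. The change is still worth making, because the data are in hand and the count would replace assumption with fact.

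**What to change.** - Extend criterion 8 to OAC charges in CDM during the 6-month pre-hospitalization period. Keep PAC on LRx or Dx, so that routine inpatient heparin does not exclude patients.
- State how the prophylaxis exception applies to CDM records. For knee or hip replacement, use charge dates relative to surgery in place of prescription duration. For medically-ill stays, do not treat the first CDM charge as proof of a new start.
- Report the patients removed by the CDM search as a separate attrition line, by cohort.
- Repeat the persistence and clinical-outcome analyses excluding every patient with any prior CDM OAC charge, whether or not exempted. A diagnosis code for long-term anticoagulant use may be added to this sensitivity analysis, as an option only.

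The cost is a few lines of eligibility text and one lookup in a file that is already linked and already searched over the same 6 months for criteria 4 and 5. A few patients are lost, including some with only brief in-hospital use. The preliminary attrition review is a natural place to make the change.

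### Exclusion criterion 8 limits prophylactic anticoagulant use to 42 days after knee/hip replacement but sets no duration limit after a 'medically ill' admission, so some longer new courses pass as prophylaxis

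*Combined protocol and SAP*

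**What the plan says.** Section 9.1.2, criterion 8, excludes patients "With use of OAC or PAC (in LRx or Dx) (unless prophylactic) during the 6-month pre-hospitalization period". Its note then defines prophylactic use by two branches joined by OR.

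- **Surgery branch.** "The OAC or PAC prescription claim will be considered prophylactic if duration of the prescription is ≤ 42 days". Treatment must also begin no earlier than 2 days before the joint replacement and no later than 7 days after it.
- **'Medically ill' branch.** "Start date of OAC or PAC occurred within 7 days after the admission of a hospitalization associated with 'medically ill" (a primary discharge diagnosis on a code list held separately), "AND with a ≥ 3 -day length of stay of the hospitalization".

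The 42-day figure appears only in the first branch, and no other section supplies a limit for the second.

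Objective 2 in Section 8 concerns treatment patterns "among patients who started on apixaban or warfarin in the hospital". Section 9.1.1, criterion 2, takes the first inpatient record of the drug as the start of treatment, without reference to earlier exposure.

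**The concern.** Criterion 8 is the plan's only direct screen for anticoagulant use before the index admission. If one branch has no duration limit, a therapeutic course can be labelled prophylactic and a prior user enters a cohort meant to be starting treatment.

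The other criteria do not fully close this gap. Criterion 1 removes "Patients with hospitalization with a primary diagnosis of VTE in the 6-month pre hospitalization period", so an earlier VTE coded as a secondary diagnosis passes. Criteria 4 and 5 remove atrial fibrillation/flutter and mechanical valves, but not other reasons for a long course.

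Two results could be affected, in different patients:

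- A patient who still holds supply may have no OAC claim within 30 days of discharge and fall into the no-OAC group (Section 9.2, item 3).
- A patient who does fill the same drug joins the outcome cohort. The treatment index claim may then continue an earlier course, so persistence is not measured from the true start.

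The plan would not show either. The medications of interest in Section 9.2.1 omit OAC and PAC, the covariates in Section 9.6 name no prior-anticoagulant term, and no count of patients retained through the exception is promised.

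**Working it through.** The plan gives no figure to reproduce, so the check is one of logic.

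**Rule as written.** Prophylactic = (duration ≤ 42 days AND start from 2 days before to 7 days after knee/hip replacement) OR (start within 7 days after a 'medically ill' admission AND stay ≥ 3 days).

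**Unit of test.** The note opens by speaking of the prescription claim, which suggests testing each claim. The second branch speaks of the start date of OAC or PAC, which allows the whole course to be judged by its first start. The text does not choose, so both were tried.

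**Test cases (hypothetical).** Day 0 is a 'medically ill' admission with a stay of at least 3 days. The first fill is on day 5, except in the last row. All fills shown fall in the 6-month look-back. In the last column the course-level test uses total days' supply.

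| Fill history | As written, each claim tested | As written, course tested by first start | 42 days in both branches (either unit) |
|---|---|---|---|
| One 30-day fill | stays in | stays in | stays in |
| One 42-day fill | stays in | stays in | stays in |
| One 90-day fill | **stays in** | **stays in** | excluded |
| Five 30-day fills (5 × 30 = 150 days) | excluded: second fill starts on day 35 | **stays in** | excluded |
| Two 90-day fills (2 × 90 = 180 days) | excluded: second fill starts on day 95 | **stays in** | excluded |
| 30-day fills from day −20 | excluded | excluded | excluded |

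So the single 90-day fill passes under both units, the refilled courses pass only on the course reading, and therapy already running before the medical admission never passes.

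**How a retained patient reaches the no-OAC group.** Suppose a 90-day fill on day 5, index VTE admission on day 30 and discharge on day 35.

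- Supply runs out at about day 5 + 90 = 95.
- The post-discharge window closes on day 35 + 30 = 65.
- The patient therefore has supply throughout the window and may file no OAC claim.
- Inclusion criterion 6 needs one LRx claim for any drug and one Dx claim after discharge, so the patient can still be in the sample.

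In general, a 90-day fill covers the whole window only if dispensed no more than 90 − 30 = 60 days before index discharge.

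**Upper bound on prior exposure.** The look-back is about 181 to 184 days. A course that begins by day 7 of a qualifying stay within it could run for up to about 6 months before the index admission.

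**The case against.** **The 42 days may be meant for both branches.** This is grammatically possible, but it is the less natural reading: the limit is tied by AND to the surgery window, and the second branch follows OR with its own two conditions. If it is the intention, one clause settles it. The 'medically ill' code list is not in the document, so which admissions qualify cannot be checked.

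**A per-claim test closes most of the gap.** This stands in part. If each claim is tested, monthly refills start outside the 7-day window and the patient is excluded. What remains is a single long-supply fill, which is recent use and not shown to be long-term therapy.

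**Stronger readings that the documents do not support.** A reader might infer that patients on long-term therapeutic anticoagulation in general stay in. They do not: a look-back claim before the medical admission still excludes them. A reader might also infer that prior VTE is the likely reason for courses entering this way. It is a possible route, but nothing shows how often it meets this narrow timing.

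It is also tempting to quantify the bias as share × (ratio − 1). A share of 1% to 5% with event rates 2 to 3 times those of new starters would give 0.01 × 1 = 1% to 0.05 × 2 = 10% inflation. Neither input is in the documents, and the direction is assumed. One share also cannot drive both harms, since patients in the no-OAC group do not contribute to persistence or recurrence rates.

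**A review step exists.** Section 9.1.2 provides a preliminary attrition table, after which criteria may change. It does not promise counts by branch, so the problem might not be visible there.

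**Conclusion.** The concern holds in a limited form. On the plain reading, the 'medically ill' branch restricts the start window and the length of stay but not the duration of the drug. A new course longer than 42 days can therefore be called prophylactic: a single 90-day fill under either unit of test, and a refilled course if only its first start date is tested. Such patients are analysed as starting in hospital, and some may be misplaced in the no-OAC group.

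The size is unknown. The documents count neither prior OAC/PAC users nor 'medically ill' admissions, and the effect may be small. The conclusion assumes that the 42-day limit applies only where it is written. Apart from bias, two programmers could code this criterion differently and obtain different cohorts, which is reason enough to settle the wording before extraction.

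**What to change.** 1. Reword criterion 8 so that the 42-day condition applies to both branches, tested on cumulative days' supply across refills of the course.
2. In the attrition table, report the number of patients retained and removed under each branch.
3. As a sensitivity analysis only, exclude patients whose pre-admission OAC or PAC supply runs into the index admission. This covers overlapping fills of 42 days or less, which the cap leaves in. It should not be a main criterion, because it would also remove patients whose VTE occurred during genuine short prophylaxis, whom the exception is meant to keep.

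The cost is one clause, a few attrition rows and one additional run, best settled before the attrition table is produced. Patients with longer courses after a medical admission are lost. The loss is probably small, but no count is available. Compared with a strict per-claim test, the cumulative test would also keep some refilled courses that total no more than 42 days, so the net change can go either way.
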